Subjects may be withdrawn from the study early due to complications secondary to the surgery itself such as sepsis, bowel dysfunction unrelated to narcotic use, and the need for further exploratory surgery.

Catheter dysfunction due to dislodgment or severe leakage may also precipitate early withdrawal from the study. Bleeding, infection, or need to anti-coagulate may cause premature need to remove the catheters from the patients. In these cases, the data will continue to be recorded as in the other arms; however, time of catheter removal will also be recorded.

Failure to perform an adequate block will also cause withdrawal from the study. Reasons for said failure would include: inability to visualize TAP space on ultrasound and surgical site preventing use of bilateral TAP block.

Failure to place catheter after successful bolus of local anesthetic would move patients from the CTAP group to an un-randomized single shot Bupivacaine arm. Patients will be followed until completion of the study. This data may be analyzed separate or as part of the single shot Bupivacaine group.

Failed block is a withdrawal prior to first study follow up; these patients would need to be replaced or moved to an open un-randomized arm.

Subjects may also be withdrawn from the study if at any time it is determined that they did not meet inclusion exclusion criteria.

iii Subject safety

iv Non-compliance with study visit schedule or study regimen

Subjects may be involuntarily exited from the study for failure to comply with the protocol, failure to attend follow-up visits, or for other reasons. The investigator shall arrange for an exit visit and complete the case report form for the subject to the extent there is data available.

Subjects may voluntarily withdraw from the study at any time without reason. The investigator shall make an effort to obtain an exit visit and complete the case report form for the subject to the extent there is data available. The investigator cannot require that an exit interview take place.

E2.g Data Collection and Follow-up for Withdrawn Subjects

- 1) Reason for withdrawal from study (i.e. block failure, catheter failure, drug toxicity, sepsis, patient request)
- 2) Day of withdrawal from study

Study Drug/Device

E3.a Description

The ON-Q[®] device is considered a non-significant risk device which has been marketed for postoperative pain management since 1998.

Description of Device:

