F3.d Data Collection Procedures for Adverse Events

Please see Attachment L2 for data collection form. All adverse event data will be entered into Oncore ERM.

F3.e Reporting Procedures

Serious Adverse Events and adverse events that meet "severe" criteria must be directly reported within 24 hours to the Principal Investigator, and the IRB.

[name] M.D.
[contact]
[contact]
Department of Anesthesiology
Midwestern Regional Medical Center
Zion, IL

Other adverse events must be entered within 7 days of collection into the Oncore ERM.

F3.f Post-study Adverse Event

Serious Adverse Events and adverse events that meet "severe" criteria must be directly reported within 24 hours to, the Principal Investigator and the IRB.

[name] M.D.
[contact]

[contact]
Department of Anesthesiology
Midwestern Regional Medical Center
Zion, IL

Other adverse events must be entered within 7 days of collection into the Oncore ERM.

F3 Study Outcome Measurements and Ascertainment

G Statistical Plan

Interim Monitoring and Early Stopping

The Principal Investigator will utilize the Oncore ERM study management system to monitor the study.

The study may be stopped early for the following reasons:

- withdrawal of funding
- safety issues
- drug has been proven effective and no further testing is needed

Analysis Plan

The study is a prospective, randomized, open, active controlled clinical trial. Effectiveness of the Continuous TAP (CTAP) via the ON-Q[®] Pain Management System will be evaluated and compared to single shot techniques with respect to reductions in postoperative opioid consumption over the first 72 hours postoperatively. Secondary outcomes including hospital length of stay (LOS), time in PACU, pain at rest and with activity, return of bowel function, and incidence of opioid related side effects will also be evaluated.

The aims of this study are to compare the efficacy of continuous TAP block via ON-Q[®] system versus that of single injection techniques for TAP block regarding opioid reduction among patients undergoing major abdominal surgery. It is hypothesized that a continuous TAP block technique reduces pain, the need for opioids as well as the expected length of stay relative to those resulting from those subjects receiving a single TAP injection of Exparel (liposomal Bupivacaine) or single TAP injection of Ropivacaine to treat postoperative pain.

Study success criteria:

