Patient characteristics and outcomes data will be summarized by cross-tabulation (categorical variables), quartiles (median, ordinal variables), and mean and standard deviation (continuous variables). Comparisons between groups will use Chi-square test or Fisher's exact test as appropriate for categorical variables and t-test or Wilcoxon rank-sum test as appropriate for continuous variables.

Analyses of primary outcome will examine differences in mean opioid consumption between the single shot TAP group and the Exparel TAP group. Analyses of secondary outcomes will examine differences in mean opioid consumption between the single shot TAP group and continuous TAP group. Treatment groups will be compared using a

student's t-test if data are normal distributed or Wilcoxon rank-sum test if not normal distributed.

The differences in mean opioid consumption across three groups (single shot TAP, continuous TAP, and Exparel TAP) will be examined with a test of means between groups using one-way analysis of variance (ANOVA). A comparison between continuous TAP and Exparel TAP will be performed. A t-test will be used if the observations in each trial arm are normally distributed; if non-normally distributed, then rank-based methods such as Wilcoxon rank-sum test will be employed.

All tests will be two-sided.

The overall incidence of serious adverse events and adverse events and number and proportion of patients reporting such events will be summarized by treatment group. Adverse events will be tabulated and summarized by the number and percentage of subjects who experienced the event.

Missing Outcome Data

Analysis will be conducted as described in prior section. Missing data will not be included in the analysis; however, may lead to an increase in patients recruited into one or more study arms.

Unblinding Procedures

This study is not blinded because it will be obvious to all care givers whether or not the patient received a continuous block with catheters or not.

H Data Handling and Record Keeping

Confidentiality and Security

Data will be collected on the data collection forms located in Attachment L9 and entered into the Oncore ERM study management system.

Data collection forms will be stored at each respective study site within a locked cabinet in a locked research office.

The Oncore ERM study management system is a secure web-based management system that is password-protected. Access to data is role-specific.

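### Patients may be withdrawn from the study for post-operative complications with no outcome recording required afterwards, and missing outcomes are left out of an analysis described as intention-to-treat

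*Combined protocol and SAP*

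**What the plan says.** **Withdrawal.** Early Withdrawal of Subjects (section E) is permissive and concerns the study as a whole: patients may leave it early because of "complications secondary to the surgery itself such as sepsis, bowel dysfunction unrelated to narcotic use, and the need for further exploratory surgery". These events arise after randomisation.

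**Data after withdrawal.** E2.g, the section on data collection and follow-up for withdrawn subjects, has two items. The first is "Reason for withdrawal from study (i.e. block failure, catheter failure, drug toxicity, sepsis, patient request"; the second is "Day of withdrawal from study". Elsewhere in the withdrawal text, patients exited involuntarily for non-compliance, missed visits or other reasons get an exit visit and a case report form completed as far as data exist. For voluntary withdrawals this is attempted.

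**Continued recording.** For catheter dysfunction or removal the plan says: "In these cases, the data will continue to be recorded as in the other arms". Patients whose catheter could not be placed are followed to completion. No such rule is given for surgical complications.

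**Outcomes.** Section C sets the primary aim on narcotic use over 48 hours. The Analysis Plan (section G) speaks of 72 hours and adds that "return of bowel function, and incidence of opioid related side effects will also be evaluated".

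**Analysis.** The Statistical Analysis Plan promises intention-to-treat with all randomised participants. If endpoints cannot be evaluated, it adds a per-protocol analysis and an analysis of non-evaluation. Missing Outcome Data says: "Missing data will not be included in the analysis", and allows extra recruitment instead.

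**The concern.** Leaving the study is treated as a consequence of a complication, when only consent withdrawal or true loss of contact needs to end data collection. In the two single-injection arms, which form the primary comparison in Sample Size, the block is a one-time injection. No study treatment remains to be stopped, so withdrawal there only loses data.

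The loss is unlikely to be random. Under Benefits in E2.f, the protocol expects lower narcotic use to speed bowel recovery and better pain control to lower the risk of pulmonary infection. On its own reasoning, events of the kind that permit withdrawal could differ by arm.

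The bowel criterion is the sharpest case. Dysfunction judged unrelated to narcotics is a ground for withdrawal; dysfunction attributed to narcotics is not. Return of bowel function is itself an outcome, so retention depends on a judgement close to what is being measured, in a study that Unblinding Procedures describes as not blinded.

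At stake is whether the opioid and bowel results compare the randomised groups, or only the patients who stayed.

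**Working it through.** **1. The planned figure.** Inputs from Sample Size: difference 4.1 − 2.4 = 1.7 mg, SD 3 mg, two-sided 5% level, 80% power.

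n per arm = 2 × [3 × (1.960 + 0.842) / 1.7]² = 48.9, rounded up to 49. The plan's 49 is reproduced. It recruits 53 per arm.

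**2. Can the rules be followed together?** Take a single-injection patient withdrawn for sepsis on the first post-operative day.

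| Text | Consequence |
|---|---|
| Early Withdrawal of Subjects | The patient may leave the study; data to exit may be kept |
| E2.g | Reason and day are recorded; no later outcome is asked for |
| Missing Outcome Data | The absent 48-hour total is left out |
| Statistical Analysis Plan | The patient must be in the analysis |

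The last two rows conflict, because no total exists and no method is given to supply one. Withdrawal after 48 hours leaves the 48-hour total intact but loses the 72-hour one. Extra recruitment restores numbers, not comparability, because the replacements are again subject to selection by complication.

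**3. Illustrative bias.** The documents give neither a complication rate nor opioid use in withdrawn patients, so these inputs are assumed. Let w_C and w_E be the proportions withdrawn before 48 hours in the control and Exparel arms, and D the excess mean use of withdrawn over retained patients, equal in both arms. For the control-minus-Exparel difference:

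shift = estimate from retained patients − estimate from all randomised = (w_E − w_C) × D

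D is varied from 1.5 to 4.5 mg (0.5 to 1.5 times the planning SD). An imbalance of 5 to 10 points is 53 × 0.05 = 2.65 to 53 × 0.10 = 5.3 patients.

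| Imbalance | D | Size of shift | Share of 1.7 mg |
|---|---|---|---|
| 5 points | 1.5 mg | 0.075 mg | 4% |
| 10 points | 1.5 mg | 0.15 mg | 9% |
| 5 points | 4.5 mg | 0.225 mg | 13% |
| 10 points | 4.5 mg | 0.45 mg | 26% |
| 0 | any | 0 | 0 |

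More withdrawals on Exparel overstate its benefit; more on control understate it.

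**4. Alternative assumption.** Suppose a complication doubles use, the plan's means describe uncomplicated patients, and all complicated patients are lost. The difference among all randomised is 4.1(1 + p_C) − 2.4(1 + p_E), where p_C and p_E are the complication rates; among retained patients it is 1.70.

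- 10% and 10%: 4.51 − 2.64 = 1.87, error −0.17 mg
- 15% and 5%: 4.715 − 2.52 = 2.195, error −0.495 mg
- 5% and 15%: 4.305 − 2.76 = 1.545, error +0.155 mg

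**5. Type I error.** With no true effect, 49 analysed per arm and SD 3, the standard error is 3 × √(2/49) = 0.606 mg. A 10-point imbalance with D = 3 mg gives a shift of 0.30 mg and a two-sided error of about 8%. With D = 4.5 mg the shift is 0.45 mg and the error about 11.5%.

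**The case against.** The plan is less severe than a quick reading suggests. A reader might infer that complicated patients are automatically removed, that only a reason and a day survive, that their safety data vanish, and that unmasked staff decide. The documents do not support that reading.

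- Withdrawal is something that may happen, not something that must.
- The case report form clause covers involuntary exits for other reasons, so data up to exit are plausibly kept.
- Exclusion from analysis is inferred from the missing-data sentence. The plan nominally includes all randomised patients and adds an analysis of non-evaluation.
- Sepsis or drug toxicity that leads to withdrawal is itself an adverse event under F3.c. Serious and severe events must be reported within 24 hours, including post-study (F3.e, F3.f), and withdrawn patients are not exempted. Any safety loss is confined to later, less severe events.
- No decision-maker is named, and E2.e masks floor nurses between the two single-injection arms.
- Asking for a reason and day after catheter failure does not strictly contradict continued recording in catheter cases.
- The bias figures are assumption-driven. With equal withdrawal and equal excess use the shift is zero, and in the doubling scenario the retained difference is 1.70 mg by construction.

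All of this stands. It narrows the point without removing it. Discretion leaves more room for selection than a fixed rule would. Data to exit do not provide a 48-hour total for a patient who exits on day 1. An analysis of non-evaluation describes the gap but does not fill it. Partial masking of nurses does not establish that whoever judges the cause of bowel dysfunction is masked.

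**Conclusion.** The point holds in this form: the protocol permits discretionary study withdrawal for post-operative complications, requires no outcome recording afterwards outside the catheter cases, and omits the resulting missing outcomes while promising intention-to-treat. For patients withdrawn before 48 hours these statements cannot all be met. The bowel criterion adds selection on a judgement tied to a trial outcome.

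Neither the size nor the direction of bias can be derived from the documents. The 0.075 to 0.45 mg range (4% to 26% of 1.7 mg) rests on an assumed 5 to 10 point imbalance and an assumed 1.5 to 4.5 mg excess. It shows that a difference of roughly three to five withdrawals between arms could matter; it does not predict that this will occur. No comparable estimate is available for the bowel or adverse event results.

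**What to change.** 1. In Early Withdrawal of Subjects, separate stopping study treatment from leaving the study. Record surgical complications, bowel dysfunction, re-exploration, drug toxicity and catheter failure as dated events, not as reasons to end data collection. Clinical decisions are unaffected.
2. Replace the E2.g list by extending the existing catheter rule to all arms: for every randomised patient who has not withdrawn consent for data use, take opioids, pain scores, bowel function and adverse events from the chart to 72 hours or discharge.
3. Analyse these patients in their randomised arm, and reconcile the withdrawal text, the intention-to-treat statement and Missing Outcome Data accordingly.
4. Add a sensitivity analysis that censors opioid use at re-operation.

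The cost is mainly protocol wording. The data are in the inpatient chart, and the attached data form already has columns for PACU and POD 0 to 3. The downside is some added variance, because totals may include opioids given around a re-operation; item 4 addresses that.

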Subjects will be consented using a current informed consent form that has been approved by the respective study site's Institutional Review Board. Subjects will be allowed adequate time to read the informed consent, discuss the consent with study staff and others (e.g., family members, friends, or any of their health care providers), and have their questions answered prior to signing the informed consent. In some cases, a site may not accrue study subjects but serve as a data analysis site so informed consent may be waived for that site.

Site-specific recruitment plans and consent process are outlined in Attachment L1.

E2.e Randomization Method and Blinding

Subjects that would normally be selected to receive a TAP block will be randomly assigned into one of the three arms. A random number generator will be used to generate an equal proportion of responses of the three arms. These responses will be sealed in envelope. The anesthesia provider will be allowed to open the envelope and become aware of the selected arm after the initiation of anesthesia (this would include the administration of a pre-medication or initiation of general anesthesia). Complete blinding is impossible to staff given the visual presence of a catheter in some groups versus the lack of catheters in other groups. In addition, the agent Exparel® has a milky color that is obvious to the anesthesia provider injecting it. However, the nursing staff on the floor will not be made aware of the use of Exparel® versus Bupivacaine in the single injection arms.

E2.f Risks and Benefits

i Risks

Potential physical risks include:

TAP block is a relatively low risk regional anesthesia technique with a long track record. However, any injection or insertion of a catheter into the body carries a slight risk of bleeding, bruising at injection or insertion site, and infection at injection or insertion site. Risks particular to an injection of a local anesthetic into the abdominal area would be bowel perforation, local anesthetic toxicity, and drug allergy. These risks are unlikely and similar to an abdominal paracentesis. Furthermore, the author is unaware of any episodes of bowel perforation from the administration of a TAP block.

The following are side effects have been seen with the local anesthetics Bupivacaine and Ropivacaine:

- Low blood pressure
- Nausea and/or vomiting
- Slow heartbeat
- Fever
- Pain
- Post-operative complications
- Low blood hemoglobin (anemia)

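### The analysis plan promises intention-to-treat, but the withdrawal rules take failed-catheter and failed-block patients out of their randomised arms, and nothing says which rule prevails

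*Combined protocol and SAP*

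**What the plan says.** The Statistical Analysis Plan in section G says that all analyses follow intention-to-treat and include every randomised participant in the three arms. Where there is relevant non-compliance or endpoints cannot be evaluated, it adds a per-protocol analysis and an analysis of non-compliance and non-evaluation.

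Early Withdrawal of Subjects in section E sets different rules:

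- **Failed catheter placement after a successful bolus** "would move patients from the CTAP group to an un-randomized single shot Bupivacaine arm". Of these patients it says "Patients will be followed until completion of the study", and then "This data may be analyzed separate or as part of the single shot Bupivacaine group".
- **Failed block:** "Failure to perform an adequate block will also cause withdrawal from the study". This counts as a withdrawal before the first follow-up, and "these patients would need to be replaced or moved to an open un-randomized arm". Two example reasons are given: the TAP space cannot be seen on ultrasound, and the surgical site prevents a bilateral block.
- **Catheter problems after placement:** "Catheter dysfunction due to dislodgment or severe leakage may also precipitate early withdrawal from the study". The same paragraph ends by saying that data recording continues.

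Section E3.b places randomisation after consent and before surgery. Section E2.e lets the anesthesia provider open the envelope and "become aware of the selected arm after the initiation of anesthesia". Missing Outcome Data (section G) leaves missing data out of the analysis and allows extra recruitment.

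**The concern.** Intention-to-treat on all randomised patients and the withdrawal rules cannot both be followed. For a failed catheter, analysis in the assigned arm is not among the options that section E offers. Both options alter the comparison after randomisation: one removes patients from the catheter arm, and the other also adds them to control. Failed placement can occur in the catheter arm only, so no matching group is removed from the other arms. The word *may* leaves the choice open until outcomes are known.

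Failed blocks leave the randomised set as well. The provider who judges the failure knows the allocation by then.

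The single shot group is the comparator for both Exparel and the catheter. Pooling therefore reaches the comparison that section G calls primary (Exparel against single shot) as well as the catheter comparison, which is part of the Primary Aim in section C and secondary in section G.

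**Working it through.** **Inputs from the documents.** Control mean 4.1 mg (SD 3). Catheter and Exparel means 2.4 mg (SD 1.3). SD 3 used for planning; two-sided 0.05; 80% power; 49 per arm, 53 recruited (section B, and Sample Size in section G).

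**Plan's own figure.** n = 2 × 3² × (1.960 + 0.842)² / 1.7² = 48.9, so 49 per arm. It reproduces.

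**Assumed, because the documents do not give them.** Failure share f among catheter patients: 2, 5 or 10% (about 1, 3 or 5 of 53). Mean m in failures: varied below.

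**1. Catheter against control at the planned means**

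- As randomised: 4.1 − [(1−f) × 2.4 + f × m]
- Pooled with control: (4.1 + f × m)/(1+f) − 2.4
- Analysed separately: 4.1 − 2.4 = 1.70 mg

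At f = 10%:

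| m (mg) | As randomised | Pooled | Separate |
|---|---|---|---|
| 3.0 | 1.64 | 1.60 | 1.70 |
| 4.1 | 1.53 | 1.70 | 1.70 |
| 6.1 | 1.33 | 1.88 | 1.70 |

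Setting pooled equal to as-randomised gives a break-even m of 3.24, 3.23 and 3.21 mg at f = 2, 5 and 10%. Pooling favours the catheter above about 3.2 mg and works against it below. Separate analysis favours the catheter when m is above 2.4 mg.

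**2. Type I error with no true effect** (all arms average 4.1 mg, 53 per arm, SD 3, failures at m = 5.1 or 6.1 mg)

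Remaining catheter patients average r = (4.1 − f × m)/(1−f). Pooled control averages c = (4.1 + f × m)/(1+f). The bias is c − r if pooled, 4.1 − r if separate, and c − 4.1 for Exparel against pooled control. The rejection rate comes from the noncentral t distribution, with arm sizes 53(1−f), 53 or 53(1+f) as applicable.

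Example, f = 10% and m = 6.1: r = 3.49/0.9 = 3.88; c = 4.71/1.1 = 4.28; bias 0.40 mg pooled, 0.22 separate, 0.18 Exparel.

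| Failures | Catheter, pooled | Catheter, separate | Exparel, pooled |
|---|---|---|---|
| 2% | 5.1-5.2% | 5.0-5.1% | 5.0-5.1% |
| 5% | 5.3-6.3% | 5.1-5.4% | 5.1-5.3% |
| 10% | 6.3-10.5% | 5.4-6.6% | 5.3-6.2% |

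Separate analysis leaves the Exparel comparison unchanged.

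**3. Choosing after the fact.** If failure is unrelated to prognosis, neither option alone inflates the error. Taking whichever is significant, with 5 of 53 failures, gave about 5.9% in 100,000 simulated null trials; a second run of 40,000 gave 5.6% for the catheter and 5.9% for Exparel.

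**4. Power of the as-randomised catheter analysis** (49 per arm, failures respond like control, normal approximation)

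Difference = 1.7 × (1−f). Power = Φ(difference/SE − 1.96).

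- SD 3 in both arms: SE = 3 × √(2/49).
- SD 3 in control and 1.3 in successful catheters: catheter-arm variance = (1−f) × 1.3² + f × 3² + f(1−f) × 1.7². At 10% this is 2.68, so SE = √((9 + 2.68)/49) = 0.488 and power = Φ(1.53/0.488 − 1.96) = 88%.

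| Failures | Difference (mg) | SD 3 in both | SD 3 and 1.3 |
|---|---|---|---|
| 0% | 1.70 | 80% | 95% |
| 5% | 1.62 | 76% | 92% |
| 10% | 1.53 | 71% | 88% |
| 15% | 1.45 | 66% | 83% |

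**The case against.** The best defence is that the intention-to-treat statement covers all analyses and so overrides section E, or that section E only describes the supplementary analyses. No text says either. Counting catheter-arm patients as controls is also an as-treated reassignment, not a per-protocol exclusion.

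Several stronger readings are tempting, and here the other side is right:

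- **That the trial is shown to be biased towards the catheter.** It is not. The direction turns on opioid use in failures, which is not given. The 10.5% figure needs 10% failures, 2 mg above average, and pooling. The BMI >40 exclusion, made because of difficulty in placing catheters, may keep failures rare.
- **That the primary Exparel result is seriously affected.** Under the same assumptions its type I error stays at 5.0-5.3% for 2-5% failures if pooled, and is untouched if failures are analysed separately.
- **That failed blocks differ by arm.** The two named reasons are not tied to an arm, since all three use bilateral ultrasound-guided blocks. The list is open and the provider knows the allocation, so some risk remains, in an undetermined direction.
- **That data stop after dislodgment or leakage.** The sentence on continued recording closes that same paragraph and plausibly covers both.
- **That intention-to-treat leaves the catheter comparison underpowered.** The 71% at 10% failures rests on the conservative SD. With the plan's own catheter SD it is about 88%.

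**Conclusion.** The contradiction stands and must be resolved. It rests on the wording: two incompatible rules for who is analysed in which arm, with discretion left open and nothing confining the section E rules to supplementary analyses. It does not rest on a demonstrated bias. At 2% failures the effect is negligible. At 10% with poor-prognosis failures it is material for the catheter comparison and modest for Exparel. All these sizes depend on an assumed failure rate and assumed opioid use in failures.

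As-randomised analysis looks feasible for failed catheters, who are followed to completion. It is not secured for failed blocks. Section E2.g asks only for the reason and day of withdrawal. The exit provision, to "complete the case report form for the subject to the extent there is data available", does not guarantee opioid totals, and Missing Outcome Data would then exclude these patients.

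**What to change.** - In Early Withdrawal of Subjects, delete the option to analyse failed-catheter patients separately or with control in the main analyses.
- State there and in the Statistical Analysis Plan that every randomised patient is analysed in the assigned arm for all comparisons; that replacements do not remove the replaced patients from the intention-to-treat set; and that as-treated, per-protocol and non-compliance analyses are supplementary.
- Record opioid totals through 72 h for failed-block and other withdrawn patients, unless consent to data collection is withdrawn. This covers the 24, 48 and 72 h endpoints. Use the same data form as for other patients (PACU, POD 0-3). That form is by postoperative day, not elapsed hours, so derive the totals in the same way for everyone.
- Confirm that continued recording covers dislodgment and leakage.

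**Cost.** Wording, a little more data entry, and the dilution of the catheter comparison shown in the power table. Failed catheters do not reduce power for the Exparel comparison. Keeping failed blocks dilutes both comparisons slightly: if 5% in each arm fail and respond alike, 1.70 mg becomes 0.95 × 1.70 = 1.62 mg.
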